Sample size for Phase 2: In Phase 2, we will conduct 12 groups (6 MAP and 6 CBT-CP) with 7 - 8 Veterans in each group to examine the feasibility of a future RCT and preliminary response to MAP (year 3 = 4 groups; year 4 = 6 groups; year 5 = 2 groups). Anticipating up to a 20% attrition rate, 86 participants will be recruited for Phase 2.

Number of Visits: Visit 1: Consent, MINI, baseline measures and actigraphy; Visits 2 - 9: MAP or CBT-CP sessions 1 - 8; Visit 10: Posttreatment measures, actigraphy; Visit 11: 3-month follow-up measures (may be done by phone); Visit 12: 6-month follow-up interview using Microsoft Teams.

Interventions. An overview of the MAP intervention is described below, as well as the CBT-CP intervention. Both groups use an 8-week, 90-minute session protocol. The MAP intervention will be delivered solely by the PI. The PI is a licensed clinical psychologist with several years of experience conducting group and individual therapy for chronic pain using mindfulness-based techniques. For the CBT-CP intervention (Phase 2 only), we will use a manualized protocol developed at the VASDHS used in previous research (Wetherell et al., 2011). In the second half of Year 2 of the award, a part-time study therapist will be hired and trained to deliver the CBT-CP intervention. This therapist will be required to have graduate (at least master's level) training in psychology, and will be recruited within the expansive VASDHS and UCSD communities. The study therapist will be supervised by [name] (co-investigator), who is a certified CBT-CP VA provider and the current supervisor for trainees in the Behavioral Medicine clinic that provide group-based CBT-CP at the VASDHS. [name] will train the study therapist and ensure competency prior to the start of Phase 2. The study therapist will have weekly check-ins with [name] via in-person or telephone while facilitating CBT-CP groups to ensure minimal drift from the protocol and to answer any questions that arise.

Description of MAP

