- Brief Pain Inventory (BPI; Cleeland & Ryan, 1994). The BPI consists of two subscales: pain severity (4-items) and pain interference (7-items). This questionnaire will be administered at the baseline assessment, weekly during the intervention (using the Polls function on WebEx), and at the post-intervention assessment. The Polls function on WebEx allows for participants to complete the BPI at the beginning of the session. Participants cannot see the responses of others. The Polls are saved on the PI's R drive located behind the VA firewall.

- Chronic Pain Acceptance Questionnaire (CPAQ; McCracken, Vowles, & Eccleston, 2004). 20-items

- Pain Catastrophizing Scale (PCS; Sullivan Bishop, & Pivik, 1995). 13-items

- Medical Outcomes Study 12-Item Short Form Health Survey (SF-12; Ware, Kosinski, & Meller, 1996). 12-items

- Patient Health Questionnaire (PHQ-9; Spitzer, Kroenke, & Williams, 1999). 9-items

- PTSD Checklist for DSM-5 (PCL-5; Bovin et al., 2016). 20-items

- Mindful Attention and Awareness Scale (MAAS; Brown & Ryan, 2003). 15-items

- Adverse Childhood Experience Questionnaire (ACE; Centers for Disease Control and Prevention, 2008). 10-items

- Injustice Experience Questionnaire (IEQ; Sullivan et al., 2008). 12-items

- Cognitive Fusion Questionnaire (CFQ; Gillanders et al., 2014). 7-items

- Insomnia Severity Index (ISI; Morin, 1993). 7-items

- Chronic Pain Values Questionnaire (CPVQ; McCracken & Yang, 2006). 12-items

- Medication will be recorded at the baseline (Visit 2) and post-intervention assessments (Visit 11). Participants will be asked to have all medication bottles, including over-the-counter medications and dietary supplements, available at their assessment appointments.

- Medication/treatment changes and adverse events will be assessed weekly. Participants will be asked if they made any medication/treatment changes over the last week and if any adverse events occurred.

- Actigraphy. The Actiwatch Spectrum PRO (Phillips Respironics, Bend, Oregon) will be used as an objective measure of physical activity. The Actiwatch Spectrum PRO will be worn continuously on the non-dominant wrist for two one-week periods at baseline and post-intervention in both phases by all participants.

-6-month interview questions:

Example questions:

1. What has been the most helpful part of the group for your pain?
2. When engaging in day-to-day activities, how are you able to manage pain?

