3. What influence has the intervention had on your amount of physical activity?
4. What strategies did you learn from the group that you are currently using?
5. How has your relationship with pain changed since being in the group?

Section 9.9 Data Safety Monitoring Board or Plan

9.9) Provide a Data Safety Monitoring Plan (DSMP) or the details of a Data Safety Monitoring Board; if a written plan is available, attach a copy of the plan to the submission form.

The Data Safety and Monitoring Board (DSMB) is comprised of Drs. [name], [name], and [name]. Drs. [name], [name], and [name] are not associated with this research project and work independently of the PI, so they are able to monitor the trial independently.

They are qualified to review the patient safety data generated by this study because of their unique experience in chronic pain management ([name]), mindfulness-based interventions ([name]), and biostatistics ([name]).

Drs. [name] and [name] will report to the DSMB on an annual basis.

Section 9.11 Pictures and Audio/Video Recordings of Patients

9.11) Describe the purpose of photographs (facial), or audio, or video recordings of patients. Describe whether the recordings will contain, or potentially contain, identifiers. Note: use of photographs or recordings must be covered in the informed consent process and documented consent documents (e.g., consent form, information sheets, telephone screen scripts).

In Phase 1, the phone calls that occur at mid-treatment and post-treatment will be audio-recorded for qualitative data analysis purposes. [name] and the PI will be in charge of these analyses under the supervision of [name]. [name] will complete the phone calls in her private office, and will record the conversation via a Sony ICDPX312 Digital Voice recorder by using the speaker-phone option. The Sony ICDPX312 Digital Voice recorder is compliant with VHA regulations, and often used as VASDHS for research and clinical purposes.

In Phase 2, audio-recordings will be made for all sessions in both treatment groups (MAP and CBT-CP) using the Sony ICDPX312 Digital Voice recorder. Audio-recordings of the MAP group will be used for quality control and to develop an adherence tracking form for future research, whereas [name] will review randomly selected recordings of the CBT-CP sessions to assure adherence to the protocol.

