Recordings from both Phase 1 and 2 will be uploaded and imported from the Sony ICDPX312 Digital Voice recorder via USB to the VA secured server system that is backed by the VA firewall. The audio recordings will be saved as MPG files and stored on the VA secured network R drive. The audio recordings will be labeled with a unique ID number, and the code key kept in a separate locked cabinet. Once the audio-recordings are uploaded and saved on the VA secured server, they will be deleted from the Sony ICDPX312 Digital Voice recorder.

Recordings from Phase 2, 6-month interviews:

We will use Microsoft Teams to record this interview session. Per Research Guidance Article KB0116766, VA investigators may use VA MS Teams to conduct remote VA research subject interviews. VA investigators are allowed to record those interviews using VA MS Teams if all applicable human subject protection regulations and policies as well as all applicable privacy laws, regulations and policies are met. We also may use the Pocket Memo Voice Recorder DPM8000 to record these interviews, which allows for audio-only recording. The Pocket Memo Voice Recorder DPM8000 has been previously approved through VA IRB.

When possible, participants will not be addressed by name during interviews, and transcribed interviews used for data analysis will deidentify participants.

Section 10 - Human Subjects

10) Describe the characteristics of the proposed subject population. Include age, gender, ethnicity, and health status as appropriate. Note: Data about people are still considered “human subjects” by the IRB, so even if you do not intend to contact the patients whose charts you will review, you still describe the characteristics related to the subjects whose charts you will review.

- Provide inclusion and exclusion criteria as appropriate. Provide a statement how non pregnancy is confirmed if pregnancy is an exclusion criteria.
- For multisite studies, provide the total number of subjects from all sites and include description of the local site's role as a coordinating center if applicable.
- Indicate the number of VA participants to be studied.
- Indicate the estimated number of consented subjects that will fail the screening process, if any.

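### The example questions for the Phase 2 six-month interview lean towards favourable answers, and none of them invites a report of no effect, unhelpful content or worsening.

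*Combined protocol and SAP*

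**What the plan says.** The Phase 2 visit list in Section 9 closes with "Visit 12: 6-month follow-up interview using Microsoft Teams". The visit before it is "Visit 11: 3-month follow-up measures (may be done by phone"), and it is the last at which scheduled measures are listed. The between-group model in Section 9 stops at post-intervention. Phase 2 participants do not complete the post-session questionnaires or the mid- and post-treatment qualitative interviews used in Phase 1.

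Section 9.8 gives five questions for the 6-month interview under the label "Example questions". They are, in order:

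- Question 1 is about benefit: "What has been the most helpful part of the group for your pain"
- Question 2 turns to coping in daily life: "When engaging in day-to-day activities, how are you able to manage pain"
- Question 3 concerns activity level: "What influence has the intervention had on your amount of physical activity"
- Question 4, paraphrased, asks for techniques taught in the group that the participant still applies.
- Question 5 closes the list: "How has your relationship with pain changed since being in the group"

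Section 9.11 says that the interviews are recorded and that "transcribed interviews used for data analysis will deidentify participants". The text gives no coding scheme, comparison or interviewer for them.

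**The concern.** An interview question that takes a benefit for granted makes it awkward to answer that there was none. If most prompts have this form and none points the other way, the transcripts will tend to yield themes of benefit whatever the participants' experience. The absence of negative themes would then tell us little.

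This matters because Section 6 presents lasting functional change as the purpose of MAP and asks whether an efficacy trial is warranted. Six-month accounts are likely to be read as evidence on whether gains last, and the text shows no quantitative measure at 6 months against which to check them.

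**Working it through.** No power, error-rate or effect-size figure bears on this point, and the plan states no figure to reproduce. The check is a classification of the five listed questions, followed by a comparison with other parts of the protocol.

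**What each question takes for granted**

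| Question | Presupposes | Can it take a null or negative answer as worded? |
|---|---|---|
| 1, most helpful part | Benefit | Only by rejecting the premise |
| 2, able to manage pain | Ability to manage, not credited to the group | Only by rejecting the premise |
| 3, influence on physical activity | No direction | Yes: none, more or less |
| 4, strategies learned and in use | Learning and current use | Only by rejecting the premise |
| 5, changed relationship with pain | Change, in no stated direction | Worsening yes; no change only by rejecting the premise |

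**Counts**

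- Benefit or uptake presupposed, strict reading: questions 1 and 4, so 2 of 5.
- Something favourable presupposed, broad reading: add question 2, so 2 + 1 = 3 of 5.
- Change presupposed without direction: question 5, so 1 of 5.
- Neutral: question 3, so 1 of 5. The total is 3 + 1 + 1 = 5.
- Direct invitation to report no effect, unhelpful content or worsening: 0 of 5.

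**Comparison with Phase 1.** Under Refinement Strategies in Section 9, the Phase 1 telephone interviews are meant to draw out negative as well as positive feedback about the facilitator. The post-session forms also let participants say that a topic was not understood or not applicable. The protocol therefore sets a more balanced standard in Phase 1 than its Phase 2 examples show, and it gives no reason for the difference.

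**Comparison with the two treatment descriptions.** Question 5 is close in idea to the acceptance process described for MAP, but its key phrase does not occur in that description. Question 2 speaks of managing pain and question 4 of strategies, and both terms occur in the description of CBT-CP. One conceptual match on the MAP side and two verbal matches on the CBT-CP side give no net direction. Section 9.8 lists one set of questions, with no arm-specific version.

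**The case against.** The strongest objection is that the interview itself is not in front of us. The five questions are labelled as examples, and Section 9.8 refers to an attachment for assessments by visit that is not among the documents. A full guide may already contain balanced probes. This stands, and the recommendation is conditional on it. The listed wording is nevertheless all that the text shows.

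Second, there are other routes for unfavourable information. Section 15 has adverse events monitored at every study contact, which would include Visit 12. The plan also records reasons for discontinuation and uses a satisfaction questionnaire. This stands for harms and, in part, for dissatisfaction. As described, these routes would not show at 6 months that a participant gained nothing or gave up the techniques.

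Third, no aim, hypothesis, primary or secondary outcome, or model rests on this interview. This also stands, and it limits the consequence.

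A reader might infer three stronger points that the documents do not support:

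- **That the interview favours MAP.** The vocabulary comparison points both ways, and the favourable prompting reaches both arms.
- **That four of the five questions assume something positive.** This requires counting question 5, which assumes change but not improvement.
- **That the interview can hardly register no effect or worsening.** All five questions are open-ended; question 3 can take a null or negative answer and question 5 a negative one. The fair statement is that no listed question invites such an answer.

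**Conclusion.** The point holds as a matter of wording. Of the five listed questions, 2 on a strict reading and 3 on a broad one presuppose something favourable, and none asks for the opposite. The likely effect is to inflate themes of benefit in both arms; the documents do not allow its amount to be estimated. A differential effect between MAP and CBT-CP is not shown.

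The conclusion assumes that the examples are representative of the full guide and that the text shows every data collection at 6 months. If the guide already contains neutral and negative probes, the point is met. Because nothing confirmatory and no stated outcome depends on the interview, this is a cheap improvement and not a flaw in the trial's main inference.

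**What to change.** First check the full interview guide. If it already asks about no change, unhelpful content and worsening, say so in Section 9.8. If not, amend it to include, for both arms alike:

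- *What, if anything, was helpful?*
- *What, if anything, was unhelpful or made your pain, mood or activity worse?*
- *How, if at all, has the way you deal with pain changed?*

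State in Section 9 that no-change and negative themes will be coded alongside positive ones and reported by arm.

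The cost is a small amendment to the guide and a few minutes per interview. The downside is that interviews already held with the present wording must be identified and reported separately, because the two sets of answers would not be directly comparable.

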Refinement Strategies: Each MAP cycle will be refined based on qualitative and quantitative feedback from study participants. Participants will be informed of the goal of refining the intervention, and will be encouraged to provide honest feedback about their experience. Initially we will focus on the extent to which participants understand and believe in the approach, and challenges in establishing a daily meditation practice. Starting at the 2nd session, each participant will complete a brief questionnaire after each session to assess their understanding of material and satisfaction with treatment delivery. Examples of questions participants would compete after each MAP session include: Did you understand today's topic? (Yes/No; If no, please briefly explain); Did you understand the exercises and examples used in today's group? (Yes/No; If no, please briefly explain); Were you satisfied with the way facilitator explained today's topic (Yes/No; If no, please briefly explain); Is today's topic applicable to your life (Yes/No; If no, please briefly explain).

Further, at mid-treatment (between session 4 and 5) and post-intervention, [name] (co-investigator and co-mentor on CDA award) will administer a 15-20 min phone interview with each Phase 1 participant. The purpose of these phone calls is to determine 1) overall satisfaction with and perceived benefit of MAP, 2) the performance of the facilitator (the PI) and any positive or negative feedback to explore the relationship between leader characteristics and treatment effects, 3) understanding and adherence to the formal meditation practice, and 4) the ability to relate mindfulness with PF processes. Phone calls will be audiotaped in order to collect and score qualitative data. The qualitative questions were developed with input from [name] (co-mentor) and [name] (qualitative methodology consultant) and can be found in the 27. *Attachments* of this application. As themes are identified in the responses, subsequent questioning may be refined to try to elicit types of feedback that will further develop our understanding of the participants' experience and how to best achieve the goals of MAP.

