
Description of CBT-CP

As aforementioned, the CBT-CP comparison group will use an 8-week, 90-minute session, manualized protocol developed at the VASDHS and used in previous research (Wetherell et al., 2011). This protocol is based on the three-component CBT model (thoughts, feelings, behaviors) with the rationale that controlling some of the factors that contribute to pain can lead to a decreased subjective experience of pain. CBT-CP focuses on training participants to manage their pain using a variety of techniques, including pain monitoring, pacing, increasing pleasant activities, progressive muscle relaxation, thought challenging, and problem skills training. The net results of these strategies is to control pain by changing its physical, cognitive, behavioral, and emotional precursors, leading to reduced pain severity and resulting beneficial consequences on pain interference, quality of life, and physical activity. Similar to MAP, CBT-CP emphasizes the importance of at-home practice assignments to develop skills taught in session.

Treatment Fidelity

Treatment fidelity is essential to the reliability and validity of study findings as well as the eventual large-scale trial and dissemination of MAP. We will employ several strategies recommended by the National Institutes of Health Behavior Change Consortium to develop a

treatment fidelity checklist for MAP during the proposed project (Bellg et al., 2004). Treatment dose across both treatment groups will be equivalent. I will conduct all MAP sessions during both phases, and the part-time study therapist will administer all CBT-CP sessions in Phase 2. Using different therapists for the MAP and CBT-CP interventions will maximize treatment adherence and minimize contamination across groups. To ensure my competency, a portion of the time during weekly meetings with [name] (co-investigator and primary mentor on CDA) will be reserved to minimize drift from the MAP protocol.

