In order to ensure that treatment is delivered consistently throughout Phase 2, all treatment sessions will be audiotaped. A random sample of 10% of all treatment sessions, divided equally across type of intervention, will be reviewed by [name]. For the CBT-CP groups, tapes will be coded for therapist competence as well as adherence to the CBT model using a similar rating system use for a previous CBT for chronic pain trial at the VASDHS (Wetherell et al., 2011). [name] also will evaluate MAP sessions based on the treatment fidelity checklist we develop to test for feasibility of fidelity tracking. Undertaking treatment fidelity evaluations in this manner will allow me to develop the necessary skills and documents necessary to ensure treatment fidelity in future trials.

Data and Data Analysis

Phase 1: Analyses for Aim 1 will be directed toward the development of MAP and collection of data to inform modification of the treatment. Qualitative and quantitative data will be collected and analyzed to achieve this. The purpose of the qualitative data is to synthesize the information and present it to the research team in order to make modifications to the approach. Drs. [name] (qualitative methodologist consultant) and [name] have extensive experience with qualitative methods and will provide guidance for conducting these analyses. Qualitative data will be analyzed using atlas.ti, a qualitative data analysis software package frequently used by [name]. Qualitative data analysis starts with coding, a process in which quotes are marked and labeled. The labeled quotes are then sorted and grouped, so that categories, then concepts, then themes can be developed. As is often standard practice for qualitative data analysis, analysis will be concurrent with data acquisition. Quantitative data (see *Questionnaires*) will be collected to test for feasibility of assessments and to compare with qualitative data. We will first examine the data for missing values. Descriptive statistics will be used to summarize the outcomes and detect and analyze outliers, data errors, and data distribution.

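### The PI, who is the only MAP therapist, co-leads the analysis of Phase 1 interviews that partly concern his own performance, with no independent coding of that material

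*Combined protocol and SAP*

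**What the plan says.** On delivery, Section 9 (Interventions) states: "The MAP intervention will be delivered solely by the PI". The Treatment Fidelity text repeats it in the first person: "I will conduct all MAP sessions during both phases".

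On the interviews, Section 9 (Refinement Strategies) schedules them "at mid-treatment (between session 4 and 5) and post-intervention", when a co-investigator "will administer a 15-20 min phone interview with each Phase 1 participant". There are four purposes. The second is to learn about "the performance of the facilitator (the PI) and any positive or negative feedback to explore the relationship between leader characteristics and treatment effects". The other three are satisfaction and perceived benefit, understanding of and adherence to the meditation practice, and the ability to relate mindfulness to the psychological flexibility processes.

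On analysis, Section 9.11 puts a named colleague and the PI jointly in charge, under a named supervisor: "and the PI will be in charge of these analyses under the supervision of". The Phase 1 part of Data and Data Analysis adds that "analysis will be concurrent with data acquisition".

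The plan also contains safeguards. The interviewer is not the PI and, per Section 9.11, "will complete the phone calls in her private office". Participants are asked for honest feedback. Recordings carry ID numbers, with the key kept apart. Section 23 has an outside qualitative expert helping to oversee the Phase 1 analyses. Changes to MAP are agreed by consensus of the PI and co-investigators.

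**The concern.** The use of a separate interviewer suggests that the plan recognises that people speak more freely about a therapist when the therapist is not asking. Making that therapist one of two leads on the analysis gives back part of the protection. Error could enter in two ways. Participants may soften what they say if they know or assume that the PI will hear it. And criticism of how a session was led may be classed as a difficulty with the material or with the participant.

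What is at stake is the quality of the evidence for Aim 1. Of the planned Phase 1 sources, only the interviews are stated to explore how leader characteristics relate to treatment effects. MAP has one facilitator throughout both phases, so no second MAP therapist is available against whom a facilitator effect could be noticed.

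**Working it through.** **Counts**
- Phase 1 sample (Section 9, Sample Size): 4 groups × 5 participants = 20, which matches the plan's stated total of 20.
- Interviews: 20 participants × 2 = 40 recordings.
- Mid-treatment share: 20 / 40 = 50%. Each of these is made with 8 − 4 = 4 of the 8 sessions still to be delivered by the PI.
- Sensitivity: no Phase 1 attrition rate is given. As an assumption, apply the 20% upper limit anticipated for Phase 2 and let every loss fall after the mid-treatment call. Then 20 × 0.8 = 16 post-treatment interviews remain, and the share is 20 / (20 + 16) = 20 / 36 = 56%. With 0 to 20% loss, the range is 50% to 56%.
- Content: 1 of the 4 stated topics concerns the PI's performance.

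No power, sample size or alpha figure depends on this point.

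**Does any safeguard make the coding of the facilitator topic independent of the PI?**
- *Separate interviewer.* This protects the conversation, not the analysis that follows.
- *ID labels.* The PI leads groups of 5, and Section 9.8 has him administer the baseline MINI, so he would probably recognise voices. Sections 27.1d2 and 27.2e1 place recordings, and a file copy of the code key, on the PI's research drive. The sentence on de-identified transcripts in Section 9.11 stands under the Phase 2 6-month interviews, not under Phase 1.
- *Co-analyst, supervisor and qualitative expert.* They provide oversight. Nothing says that any of them codes the facilitator responses separately from the PI, or that these are double coded.
- *Consensus rule.* It governs changes to MAP. The stated purpose of the qualitative work is to synthesise the information for the research team, so consensus acts on material already classified, and the PI is part of that consensus.
- *Timing.* Concurrent analysis permits the PI to see mid-treatment comments before session 8. Nothing says that he will, and nothing prevents it.

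Each safeguard helps, but none closes this gap.

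**The case against.** The strongest reply is that this is formative, developer-led work with several checks. The interviewer is a co-investigator and co-mentor of the PI, hence not a subordinate. The analysis has a second lead, a supervisor and outside qualitative guidance. The post-session questionnaires separately ask about satisfaction with the facilitator's explanations. Prompt feedback to the facilitator is part of the method: Section 9 uses it to plan the next class session. A developer also gains little by hiding criticism that would improve the product.

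Much of this stands. It rules out saying that the separate interviewer's protection is lost, and it makes barring the PI from all recordings a debatable trade. It does not answer the narrower point that nobody is assigned to handle the comments about the PI without the PI.

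A reader might infer more than the documents support:
- *That the PI alone controls or codes the analysis.* Section 9.11 names a co-lead and a supervisor, and the coding description does not say who codes.
- *That the feedback is biased, in MAP's favour.* Only a risk is shown. Softened criticism could flatter the Aim 1 report, yet faults left in the manual could weaken MAP in Phase 2, so no direction follows.
- *That the PI hears criticism before sessions 5 to 8.* This is permitted, not stated.
- *That participants know the PI will listen.* This cannot be checked, because the consent pages are not available.
- *That the Phase 2 6-month interviews share the problem.* Their analyst is not named, the example questions have no item on facilitator performance, and treatment is over by then.

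**Conclusion.** The role conflict is real and the plan does not address it. The sole MAP therapist co-leads, under supervision, the analysis of interviews in which one of four topics is his own performance. Half of the 40 planned interviews are recorded mid-treatment, and neither independent coding of that topic nor delayed access to it is provided for. The result is a risk, of unknown size and direction, that criticism of the facilitator is softened or misclassified.

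The effect is confined to Aim 1. Phase 2 has no such mid- or post-treatment interviews, and no Phase 2 outcome analysis uses the Phase 1 ones. This is a cheap improvement and not a flaw that undermines the trial.

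The conclusion assumes that the attachments and consent material do not already assign this coding elsewhere. Because names are masked, it cannot be confirmed that the Section 9.11 supervisor is the qualitative expert of Section 23.

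**What to change.** Add to Section 9.11:
- The co-analyst already named codes the facilitator-performance and leader-characteristics responses without the PI, under the existing supervision.
- The PI receives these responses only as de-identified themes. Mid-treatment comments about the facilitator are released after that group's last session and in time for the refinement meeting in the month between cycles.
- The PI may keep his role in the analysis of the other three topics, so feedback on content can still shape the next session.

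Phase 1 may already be over: the form is dated 12/12/2023, and cohort 3 was due to finish in March 2020. Completion is not stated. If it is complete, a non-PI analyst should re-code the facilitator segments from the retained recordings (Section 27.4c describes six-year retention after closure), and the PI's role should be disclosed when Aim 1 is reported.

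The cost is protocol wording and some coding time moved to a team member already assigned to this analysis. The downside is that the PI gets feedback on this one topic later and second-hand. No change to the Phase 2 6-month interviews is needed on this ground.
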